#### **4.3.6. Other Secondary Efficacy Endpoints**

The other secondary endpoints will rely upon imputed values utilized for the primary and key secondary efficacy endpoints where applicable (BMI/BMI Z-Score/BMI P95/Weight/weekly average in daily hunger). Endpoints relating to domains that have not previously relied on multiply imputed values will be analyzed as observed. Any analyses relying upon imputed values will specify so in the sections below.

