### **3.10. Missing, Unused, and Spurious Data**

Missing data will be handled for height and body weight and, by extension, their derivatives (BMI, BMI Z-Score, BMI P95), daily hunger scores, and adverse event dates.

Imputation of other missing questionnaire data will be applied for the derivation of summary scores, dependent on the questionnaire and imputation rules of the questionnaire.

Unless otherwise specified, all other study data will be summarized as reported (missing data will not be imputed).

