#### 4.3.1. Primary Estimand

The population of the primary estimand is among participants (aged 4 years or older) with documented evidence of acquired HO and weight gain according to the inclusion/exclusion criteria. Participants will receive either active setmelanotide or placebo, where dose-escalation will occur based upon an **CCI** [REDACTED]. The primary analysis will be executed using the mITT analysis set, including all randomized patients receiving at least one dose of study drug, grouped as randomized.

The variable is mean percent change from baseline in BMI after 52 weeks of treatment with either setmelanotide or placebo.

Intercurrent events: Patients who discontinue treatment prior to study discontinuation will be handled via the treatment policy strategy, in which all collected measurements will be included in the statistical analyses. Other potential intercurrent events such as receiving the wrong treatment, treatment interruption, and non-adherence to study drug will also be handled via the treatment policy strategy whereby all collected measurements will be included in the statistical analyses.

Any on-study death will be handled via the composite strategy, in which death is considered a sufficiently unfavorable outcome and the patient will have their corresponding change and percent change from baseline artificially set to 0.

The population level summary is the difference between treatment groups (setmelanotide and placebo) in mean percent change from baseline in BMI at Week 52, obtained from an analysis of covariance (ANCOVA) model, with unequal variance to account for possible unequal residual variances, based on the outcomes of 100 imputed datasets combined using Rubin's Rule (Little and Rubin 2002). Multiple imputation assuming missing not at random (MNAR) will be used as the primary approach for missing data and will model the missing measurements based on known measurements from retrieved dropouts in the same treatment group. If insufficient retrieved dropouts exist to provide a reliable multiple imputation model, wash-out imputation will be used where missing values for subjects on active drug will be imputed with observed baseline and data from the placebo group. No intermediate values from the active treatment group would be used in this approach. Further technical details are found in [Section 3.10.2](#).

The robustness of the primary estimand will be assessed through sensitivity analysis using two-dimensional tipping point.

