##### **4.3.6.2. Symptoms of Hyperphagia (Patient/Caregiver Versions)**

Daily Symptoms of Hyperphagia scores are recorded for 7 consecutive days before each scheduled trial visit.

Patients  $\geq 12$  years of age who are able to self-report CCI [REDACTED]  
[REDACTED]  
[REDACTED]  
[REDACTED]  
[REDACTED]

Caregivers of patients who are  $<12$  years of age or of patients  $\geq 12$  years of age who cannot self-report will be administered CCI [REDACTED]  
[REDACTED]  
[REDACTED]  
[REDACTED]  
[REDACTED]

[REDACTED]  
[REDACTED]  
[REDACTED]  
[REDACTED]  
[REDACTED]  
[REDACTED]  
[REDACTED]  
[REDACTED]  
[REDACTED]  
[REDACTED]  
[REDACTED]

Analysis of the mean change in weekly average of symptoms of hyperphagia composite score after approximately 52 weeks will be analyzed separately for each of the questionnaires, assuming sufficient sample size, for pivotal and all patients in the mITT. The between-group comparison on the mean change from baseline will be conducted with an ANCOVA model, assuming unequal variance to account for possible unequal residual variances. The ANCOVA model will adjust for baseline score in both models with a stratification factor of age groups and subpopulations (Japanese and non-Japanese), as appropriate.

Descriptive summaries will be provided for weekly average composite score, change from baseline, and percent change from baseline for pivotal and all patients, as needed.

Subgroup analysis on the Symptoms of Hyperphagia based upon different baseline value data cutoffs may be explored as appropriate.

The Symptoms of Hyperphagia results will be presented in a by-patient listing.

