#### **4.3.6.5. Body Weight Percent Change from Baseline in Patients $\geq 18$ Years of Age**

Mean percent change in weight from baseline after approximately 52 weeks in pivotal and all patients  $\geq 18$  years in the mITT will be analyzed.

The between-group comparison on the mean percent change from baseline will be conducted with an ANCOVA model, assuming unequal variance to account for possible unequal residual variances. The ANCOVA model will adjust for the stratification factor of subpopulations (Japanese and non-Japanese), as appropriate.

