#### 4.3.6.10. Waist Circumference

Change in waist circumference from Baseline after approximately 52 weeks on a therapeutic regimen of setmelanotide compared to placebo will be analyzed.

The between-group comparison will be conducted for pivotal and all patients in the mITT using an ANCOVA model adjusted with baseline measurement and a stratification factor of age groups ( $<12$  years old,  $\geq 12$  and  $<18$  years old, and  $\geq 18$  years old) and subpopulations (Japanese and non-Japanese), as appropriate.

The actual, change from baseline, and percent change from baseline for waist circumference will be summarized descriptively by visit for pivotal and all patients in the mITT, as needed.

Change from baseline in waist circumference will be presented graphically by treatment group and visit, with standard error bars included, for the mITT for pivotal and all patients. The x-axis will include visit in weeks and the y-axis will represent the observed mean  $\pm$  SE of percent change from baseline.

By-patient listing will be provided based on reported results.

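### Four secondary domains are analysed as observed in the mITT while BMI, weight and hunger are imputed: extending the SAP's own imputation to them is a cheap improvement

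*SAP*

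**What the plan says.** SAP 4.3.6 divides the other secondary endpoints in two. Some reuse the values imputed for the primary and key secondary analyses, "where applicable (BMI/BMI Z-Score/BMI P95/Weight/weekly average in daily hunger"). For the rest, "Endpoints relating to domains that have not previously relied on multiply imputed values will be analyzed as observed". SAP 3.10 sets the same default: "Unless otherwise specified, all other study data will be summarized as reported (missing data will not be imputed"). The relief it gives for questionnaires concerns deriving summary scores by each instrument's own rules, which does not supply a missing visit.

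Four domains fall under the as-observed rule: the hyperphagia composite (4.3.6.2), IWQOL (4.3.6.9), waist circumference (4.3.6.10) and cardiometabolic parameters (4.3.6.11). Each is an ANCOVA of change from baseline, and each names the mITT. For waist, "The between-group comparison will be conducted for pivotal and all patients in the mITT using an ANCOVA model adjusted with baseline measurement". For hyperphagia, the composite "will be analyzed separately for each of the questionnaires, assuming sufficient sample size, for pivotal and all patients in the mITT". The legible text of these sections mentions no imputed datasets. SAP 2.1 defines the mITT as everyone randomised and dosed. Under SAP 3.11.1 the primary timepoint is missing if no on-site result falls within days 305 to 425 from the start of the therapeutic dose. Protocol 7.5.2 lists these endpoints as Nos. 2, 9, 10 and 11 and tests them at the two-sided 0.05 level with 95% confidence intervals.

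For BMI, weight and hunger, SAP 3.10.2, 3.10.3 and 4.3.1 use a retrieved-dropout model. If there are too few retrieved dropouts, "wash-out imputation will be used where missing values for subjects on active drug will be imputed with observed baseline and data from the placebo group". For BMI the as-observed analysis is only supplementary (4.3.4.2).

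**The concern.** A single-timepoint ANCOVA on observed data uses completers and those retained dropouts who were measured in the window. It estimates the effect of assignment only if missingness is unrelated to outcome given treatment, baseline and strata. For BMI, weight and hunger in the same patients, the SAP does not rely on that assumption. The contrast is sharpest for hunger and hyperphagia. Both are recorded in the home e-diary over the 7 days before a visit (SoA footnote 17), yet a missing hunger average is imputed and a missing hyperphagia average is dropped.

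If patients who stop setmelanotide and are not measured lose the drug effect, leaving them out moves these differences away from zero. The report would then set conservatively handled BMI and hunger results beside completer-weighted waist, hyperphagia, quality-of-life and cardiometabolic results, all under one mITT label. No estimand and no missing-data sensitivity analysis is stated for the four domains.

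**Working it through.** **The plan's own figure.** The documents give no power or bias figure for these endpoints. The primary figure is about 99.5% power for a difference of -10 with SD 10, two-sided 0.05, 80:40 and 20% dropout (Protocol 7.1, SAP 3.1). Taking 20% from each arm leaves 64:32. The standard error is 10 × √(1/64 + 1/32) = 2.165, and 10/2.165 - 1.96 = 2.66, so power is 99.6% (normal) or 99.5% (noncentral t). The figure reproduces with 20% lost from both arms. The text does not say whether dropout means stopping treatment or leaving the study, and it does not split the rate by arm.

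**Inputs for the bias.**
- d = share of setmelanotide patients who drop out. The plan's 20% is used.
- f = share of the on-drug effect that dropouts keep. f = 0 is the SAP's wash-out assumption; other values are assumptions.
- r = share of dropouts with a 52-week value. This is an assumption, as the documents give none.
- Placebo dropouts resemble placebo completers, unless stated otherwise.

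**Formulas**, with the on-drug effect set to 1:
- all-patient effect = (1 - d) + d·f
- as-observed effect = [(1 - d) + d·r·f] / [(1 - d) + d·r]

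| d | f | r | All patients | As observed | Ratio |
|---|---|---|---|---|---|
| 0.20 | 0 | 0 | 0.800 | 1.000 | 1.250 |
| 0.20 | 0 | 0.25 | 0.800 | 0.941 | 1.176 |
| 0.20 | 0 | 0.50 | 0.800 | 0.889 | 1.111 |
| 0.20 | 0 | 0.75 | 0.800 | 0.842 | 1.053 |
| 0.20 | 0 | 1 | 0.800 | 0.800 | 1.000 |
| 0.20 | 0.5 | 0 | 0.900 | 1.000 | 1.111 |
| 0.20 | 0.5 | 0.50 | 0.900 | 0.944 | 1.049 |
| 0.20 | 1 | 0 | 1.000 | 1.000 | 1.000 |

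With f = 0 and r = 0 the ratio is 1/(1 - d), which passes 1.10 once d exceeds 1 - 1/1.10 = 9.1%.

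**Outside that range**, still with r = 0:
- If the overall 20% splits as 25% active and 10% placebo (20 + 4 = 24 of 120) and f = 0, the ratio is 1/0.75 = 1.33. At 30% and 0% (24 + 0 = 24 of 120) it is 1/0.70 = 1.43.
- If active dropouts end worse than placebo (f = -0.25, d = 0.20), the all-patient effect is 0.80 - 0.05 = 0.75 and the ratio is 1.33.
- If 20% drop out of each arm and placebo dropouts do worse than placebo completers by half the effect, the all-patient effect gains 0.20 × 0.5 = 0.10. With f = 0.5 the ratio is 1.00/1.00 = 1.00. With f = 0.75 it is 1.00/1.05 = 0.95, an understatement.

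**Simulation check.** In 4,000 simulated trials (80:40, SD 10, on-drug effect -10, 20% dropout per arm, f = 0, r = 0), the mean estimate was -9.97 as observed and -7.99 in all patients, a ratio of 1.248. This borrows the BMI inputs and confirms the algebra only. It is not evidence about these endpoints.

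**The case against.** Several points on the other side stand.

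- A reader might infer that everyone who stops treatment is excluded. The documents do not support that. Patients who stop are asked to continue assessments as Retained Dropouts (SAP 1.3.1, Protocol 4.3), and an as-observed analysis keeps their off-drug values. A late leaver's early-termination visit can also fall inside the 305 to 425 day window. Only patients with no value in the window are lost.
- A reader might take 25% as the expected bias or its ceiling. It is neither: it is one scenario, and the working shows ratios from 0.95 to 1.43 under other assumptions.
- A reader might infer that adult percent weight change (4.3.6.5) could be run on completers only, because that section does not mention imputed datasets. SAP 3.10.2 puts weight analyses under multiple imputation, and 4.3.6 lists weight among the imputed domains. What is missing is a cross-reference.
- The mITT label is not wrong in itself. An analysis set is distinct from missing-data handling, and 4.3.4.2 openly describes an observed-data analysis in the mITT. No protocol commitment is broken: Protocol 7.5.2 promises only ANCOVA for these endpoints, and the treatment-policy estimand is written for the primary endpoint.
- Much of SAP 4.3.6.2 and Section 5 is redacted, so a missing-data rule for hyperphagia may exist there. The point for that domain rests on the legible text.
- Requiring wash-out for every missing value would be a poor remedy. It skips the SAP's retrieved-dropout-first order and would treat a patient still on drug who missed a questionnaire as placebo-like.

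These points limit the claim. They do not remove the difference in handling between these four domains and BMI, weight and hunger, or the lack of a stated estimand.

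**Conclusion.** This is worth changing because it is cheap. It does not threaten the trial's conclusions: the four domains are outside the fixed sequence in SAP 3.7, so neither trial success nor the key secondary claims are affected.

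On the legible text, the four domains are complete-case analyses at the primary timepoint, whereas BMI, weight and hunger are imputed. The overstatement could be about 25% if 20% of setmelanotide patients have no 52-week value, keep no benefit, and placebo dropouts resemble placebo completers. With 25%, 50% or 75% of dropouts retrieved it would be about 18%, 11% or 5%. It vanishes if all are retrieved or if dropouts keep the full effect. The dropout split, the retrieval rate and the outcomes of dropouts are not in the documents, so neither the size nor the direction of the bias can be stated as fact.

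**What to change.** In SAP 4.3.6, with a matching exception in 3.10, replace the as-observed rule for the hyperphagia composite, IWQOL, waist circumference and cardiometabolic endpoints as follows.

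- Impute missing primary-timepoint values by the Section 3.10.2 approach in its stated order: the retrieved-dropout model first, and wash-out only if retrieved dropouts are insufficient.
- Restrict the visit list to each endpoint's scheduled visits. IWQOL, for example, has only Visit 4 between baseline and end of treatment.
- Do not impute patients still on treatment at the primary timepoint as placebo-like, and say how their missing values are filled.
- Combine 100 datasets by Rubin's rule where numbers permit. SAP 4.3.6.2 already makes the hyperphagia analyses conditional on sufficient sample size.
- State the estimand for these endpoints, keep the as-observed ANCOVA as supplementary, and report the number analysed in each arm.

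As an editorial clarification only, add to 4.3.6.5 a reference to the 100 imputed weight datasets used in 4.3.6.4.

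The cost is SAP wording and some extra programming on imputation code already planned, with no new data. The estimates for these endpoints would probably be somewhat smaller.

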##### **4.3.6.1. Daily Hunger Questionnaire Reduction**

The proportion of pivotal patients  $\geq 12$  years of age achieving a  $\geq 2$ -point reduction in the weekly average of daily most hunger score from baseline after approximately 52 weeks will be analyzed for the mITT. Binomial proportions will be calculated for each treatment arm for each of the 100 imputed datasets. Analysis between arms will be conducted for each of the 100 imputed datasets with a CMH test with adjustment of stratification factors of age group ( $\geq 18$  years old,  $\geq 12$  and  $< 18$  years old) and subpopulation (Japanese and non-Japanese), as appropriate. This analysis will follow the same methodology as the first key secondary efficacy endpoint as outlined in [Section 4.3.5.1](#).

This analysis will be repeated for all patients.

##### **4.3.6.2. Symptoms of Hyperphagia (Patient/Caregiver Versions)**

Daily Symptoms of Hyperphagia scores are recorded for 7 consecutive days before each scheduled trial visit.

Patients  $\geq 12$  years of age who are able to self-report CCI [REDACTED]  
[REDACTED]  
[REDACTED]  
[REDACTED]  
[REDACTED]

Caregivers of patients who are  $<12$  years of age or of patients  $\geq 12$  years of age who cannot self-report will be administered CCI [REDACTED]  
[REDACTED]  
[REDACTED]  
[REDACTED]  
[REDACTED]

[REDACTED]  
[REDACTED]  
[REDACTED]  
[REDACTED]  
[REDACTED]  
[REDACTED]  
[REDACTED]  
[REDACTED]  
[REDACTED]  
[REDACTED]  
[REDACTED]

Analysis of the mean change in weekly average of symptoms of hyperphagia composite score after approximately 52 weeks will be analyzed separately for each of the questionnaires, assuming sufficient sample size, for pivotal and all patients in the mITT. The between-group comparison on the mean change from baseline will be conducted with an ANCOVA model, assuming unequal variance to account for possible unequal residual variances. The ANCOVA model will adjust for baseline score in both models with a stratification factor of age groups and subpopulations (Japanese and non-Japanese), as appropriate.

Descriptive summaries will be provided for weekly average composite score, change from baseline, and percent change from baseline for pivotal and all patients, as needed.

Subgroup analysis on the Symptoms of Hyperphagia based upon different baseline value data cutoffs may be explored as appropriate.

The Symptoms of Hyperphagia results will be presented in a by-patient listing.

**4.3.6.3. Proportion of Patients with  $\geq 10\%$  Reduction in BMI from Baseline**

The proportion of pivotal and all patients in the mITT achieving a  $\geq 10\%$  reduction in BMI from baseline after approximately 52 weeks will be analyzed. Binomial proportions will be calculated for each treatment arm for each of the 100 imputed datasets. Analysis between arms will be conducted for each of the 100 imputed datasets with a CMH test with adjustment of stratification factors of age group and subpopulation (Japanese and non-Japanese), as

appropriate. This analysis will follow the same methodology as the first key secondary efficacy endpoint as outlined in [Section 4.3.5.1](#).

#### **4.3.6.4. Proportion of Patients with $\geq 10\%$ Reduction in Weight from Baseline**

The proportion of pivotal and all patients in the mITT achieving a  $\geq 10\%$  reduction in weight from baseline after approximately 52 weeks will be analyzed. Binomial proportions will be calculated for each treatment arm for each of the 100 imputed datasets. Analysis between arms will be conducted for each of the 100 imputed datasets with a CMH test with adjustment of stratification factors of age group and subpopulation (Japanese and non-Japanese), as appropriate. This analysis will follow the same methodology as the first key secondary efficacy endpoint as outlined in [Section 4.3.5.1](#).

The actual, change from baseline, and percent change from baseline for observed values of weight will be summarized descriptively by visit for pivotal and all patients in the mITT, as needed.

Percent change from baseline in weight in observed values will be presented graphically by treatment group and visit, with standard error bars included, for the mITT for pivotal and all patients. The x-axis will include visit in weeks and the y-axis will represent the observed mean  $\pm$  SE of percent change from baseline.

A by-patient listing of observed body weight will be provided.

#### **4.3.6.5. Body Weight Percent Change from Baseline in Patients $\geq 18$ Years of Age**

Mean percent change in weight from baseline after approximately 52 weeks in pivotal and all patients  $\geq 18$  years in the mITT will be analyzed.

The between-group comparison on the mean percent change from baseline will be conducted with an ANCOVA model, assuming unequal variance to account for possible unequal residual variances. The ANCOVA model will adjust for the stratification factor of subpopulations (Japanese and non-Japanese), as appropriate.

#### **4.3.6.6. BMI Z-Score and BMI Percentile Reduction from Baseline in Patients $< 18$ Years of Age**

BMI percent of the 95th percentile will rely upon the Center for Disease Control's (CDC) 2000 CDC Growth Chart Provided Source Code and Datasets. Similar to the macro utilized for BMI Z-score generation outlined in [Section 4.3.5.1](#), the patient age, sex, and BMI will be provided into this CDC macro. The CDC macro will utilize these inputs to generate the calculated percent of the 95th percentile which will be pulled directly into the appropriate CDISC compliant dataset.

The mean reduction in BMI Z-Score after approximately 52 weeks on therapeutic regimen in pivotal and all patients  $< 18$  years of age in the mITT and in BMI percentile in pivotal and all patients  $< 18$  years in the mITT will be analyzed. Analyses for each item will be conducted separately.

Analysis will be conducted with an ANCOVA model, assuming unequal variance to account for possible unequal residual variances and adjusted with baseline score and stratification factors of age groups (<12 years old,  $\geq 12$  and <18 years old) and subpopulation (Japanese and non-Japanese), as appropriate. The ANCOVA model will be run for each of the 100 imputed datasets and the outcomes from each of the 100 imputed datasets will be combined using Rubin's Rule to provide an overall estimate against the null hypothesis with corresponding confidence intervals and p-value.

Descriptive summaries for the BMI percentile reduction actual, change from baseline, and percent change from baseline will be provided by visit for pivotal and all patients <18 years of age in the mITT, as needed.

Change from baseline in BMI percentile reduction in observed values will be presented graphically by treatment group and visit, with standard error bars included, for the mITT for pivotal and all patients <18 years of age. The x-axis will include visit in weeks and the y-axis will represent the observed mean  $\pm$  SE of percent change from baseline.

BMI percent of 95th percentile results will be presented in a by-patient listing.

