### 4.1. Inclusion Criteria

Inclusion criteria are detailed below. CCI

Patients must meet all of the following criteria to be eligible for trial participation:

1. Patient has documented evidence of acquired HO defined as:
  - CCI
2. Aged 4 years and older at time of enrollment
3. Documented weight gain associated with the hypothalamic injury either before therapy or following therapy (surgery and/or following chemotherapy or radiotherapy), and a body mass index (BMI) of  $\geq 30$  kg/m^2 for patients  $\geq 18$  years of age, or BMI  $\geq 95^{\text{th}}$  percentile for age and sex for patients 4 to  $<18$  years of age based on the US Centers for Disease Control and Prevention criteria.
4. Patients must meet the contraception requirements outlined in Section 6.8.9 unless otherwise indicated.
5. Ability to communicate well with the Investigator, understand and comply with the requirements of the trial, and understand and sign the written informed consent and/or assent for patients aged  $<18$  years, a parent/legal guardian that can sign.
6. If receiving hormone replacement therapy (ie, thyroid hormones, glucocorticoids, growth hormone or other medications known to affect metabolism or weight/body composition), the dose of such therapy has remained stable for at least 2 months prior to Screening.  
Note:
  - Changes in dose of  $\leq 25\%$  may be permissible, with the Sponsor's approval. If results of free thyroxine (FT4) warrant changes in therapy  $>50\%$  or the addition of new medication the patient is screen failed and can be reassessed after 2 months.
  - This does not apply to patients experiencing adrenal crisis.

CCI

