### **7.5.2. Other Secondary Efficacy Endpoints**

There are 11 other secondary efficacy endpoints in the trial:

1. The proportion of patients with a  $\geq 2$ -point reduction in the weekly average of the daily most hunger score from Baseline after approximately 52 weeks on a therapeutic regimen of setmelanotide compared to placebo
2. The mean change in the weekly average of the symptoms of hyperphagia composite score from Baseline after approximately 52 weeks on a therapeutic regimen of setmelanotide compared to placebo
3. The proportion of patients with a  $\geq 10\%$  reduction in BMI from Baseline after approximately 52 weeks on a therapeutic regimen of setmelanotide compared to placebo
4. The proportion of patients with  $\geq 10\%$  reduction in weight from Baseline after approximately 52 weeks on a therapeutic regimen of setmelanotide compared to placebo.
5. Mean percent change in weight in patients  $\geq 18$  years from Baseline after approximately 52 weeks on a therapeutic regimen of setmelanotide compared to placebo

6. Mean BMI Z-score and BMI percentile reduction in patients <18 years of age from Baseline after approximately 52 weeks on a therapeutic regimen of setmelanotide compared to placebo
7. The proportion of patients aged  $\geq 4$  to <18 years with  $\geq 0.2$ -point reduction of BMI Z-score from Baseline after approximately 52 weeks on a therapeutic regimen of setmelanotide compared to placebo
8. The proportion of patients with BMI <30 kg/m^2 (patients aged  $\geq 18$  years) or <95th percentile (patients aged <18 years) from Baseline after approximately 52 weeks on a therapeutic regimen of setmelanotide compared to placebo
9. Mean change in physical functioning score and total score for the IWQOL (IWQOL-Lite-CT in patients  $\geq 18$  years and IWQOL-Kids in patients 11 to <18 years), from Baseline after approximately 52 weeks on a therapeutic regimen of setmelanotide compared to placebo.
10. Change in waist circumference from Baseline after approximately 52 weeks on a therapeutic regimen of setmelanotide compared to placebo.
11. The difference in change in cardiometabolic parameters including blood pressure, CCI [REDACTED] liver function and CCI [REDACTED] from Baseline after approximately 52 weeks on a therapeutic regimen of setmelanotide compared to placebo.

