#### **3.10.2. Weight**

For analyses of weight and its derivatives (BMI, BMI Z-Score, BMI P95), including the primary and key secondary efficacy analyses, multiple imputation (MI) will be used to model missing weight measurements at the primary timepoint (after 52 weeks of therapeutic treatment). BMI, BMI Z-score, and BMI P95 will then be derived based upon the imputed weight and available height records.

Weight will be imputed using a retrieved dropout (RD) approach utilizing the following steps:

- If non-monotone missingness is observed in the full set of observations (inclusive of on-treatment completers), Markov Chain Monte Carlo will first be utilized on the full set of observations according to treatment arm to impute intermediate values and to generate a monotone missingness pattern.

- From there, or if a monotone pattern is naturally observed in the data, 2 subsets will be generated:
  - Subset 1: patients classified as off-treatment at primary timepoint (RDs or non-RDs)
  - Subset 2: on-treatment completers
- Monotone regression MI will then be applied to Subset 1 according to treatment arm, regressing on baseline weight, Visit 2 weight, Visit 4 weight, Visit 7 weight, Visit 9 weight, Visit 11 weight, and primary timepoint weight. This will result in 100 complete Subset 1 datasets (either as result of impute = 100 MCMC and impute = 1 Monotone, or, impute = 100 Monotone, missingness structure dependent).
- The complete Subset 1 data will be combined with Subset 2 data to give a wholly complete dataset, representative of all patients (Subset 1 and Subset 2)

Should there be insufficient RD to provide a reliable multiple imputation model, a wash-out imputation method will be utilized.

For wash-out imputation, placebo patients will first be imputed assuming missing-at-random (MAR) regressing on baseline weight, Visit 2 weight, Visit 4 weight, Visit 7 weight, Visit 9 weight, Visit 11 weight, and primary timepoint weight. This accounts for planned on-site visits as well as a combined primary timepoint as outlined in [Table 3-1](#) below.

If non-monotone missingness is observed, MCMC MI will be utilized according to treatment arm to impute intermediate values and to generate a monotone missingness pattern. From there, or if a monotone pattern is naturally observed in the data, MI utilizing monotone regression will be executed.

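### SAP 4.3.6.6 derives BMI as a percent of the CDC 95th percentile but specifies the analysis on BMI percentile, so the analysed variable is not settled

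*SAP*

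**What the plan says.** **Endpoint.** Protocol 7.5.2 no. 6 is "Mean BMI Z-score and BMI percentile reduction in patients <18 years of age from Baseline after approximately 52 weeks". Protocol Table 3 and SAP 1.4.1 carry the same wording.

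**Entry rule.** Protocol 4.1 no. 3 requires a BMI at or above the 95th "percentile for age and sex for patients 4 to" under 18, "based on the US Centers for Disease Control and Prevention criteria".

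**Derivation.** SAP 4.3.6.6 opens with a different measure. BMI percent of the 95th "percentile will rely upon the Center for Disease Control's (CDC) 2000 CDC Growth Chart Provided Source Code and Datasets". The macro receives age, sex and BMI: "The CDC macro will utilize these inputs to generate the calculated percent of the" 95th percentile. The section closes with a by-patient listing of this measure.

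**Analysis.** Between those two points, the same section specifies the ANCOVA on mean reduction in Z-score for those under 18 "years of age in the mITT and in BMI percentile in pivotal and all patients" under 18. The by-visit summaries and the figure are also labelled as BMI percentile reduction.

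**Imputation.** SAP 3.10.2 says that "BMI, BMI Z-score, and BMI P95 will then be derived based upon the imputed weight and available height records". SAP 4.3.6 gives the imputed domains available to the other secondary endpoints as "BMI/BMI Z-Score/BMI P95/Weight/weekly average in daily hunger". Percentile is in neither list.

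**The concern.** A BMI percentile is a rank that cannot exceed 100. BMI as a percent of the 95th percentile is a ratio to a reference BMI and has no ceiling. The two give different treatment effects from the same data. The section defines one and names the other in its model, so two programmers could follow the text faithfully and report different results for the same endpoint.

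If percentile is used as written, every eligible child has at most about 5 points of room above the entry threshold. The mean change would be driven by children near the 95th percentile. A genuine BMI loss in the most severely obese children would hardly show, and a linear model on a bounded, skewed outcome would be hard to interpret. If P95 is used, the scale is sound, but the result would be reported under the name of another quantity.

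**Working it through.** The documents state no effect size, standard deviation or power for this endpoint, so there is no plan figure to reproduce. The check has two parts: which variable the text points to, and how much the choice matters.

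**1. The SAP text side by side**

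| SAP section | Variable named |
|---|---|
| 1.4.1 endpoint | BMI percentile |
| 3.10 and 3.10.2 missing data | P95 |
| 4.2 baseline summary | P95 |
| 4.3.6 imputed domains | P95 |
| 4.3.6.6 derivation and listing | P95 |
| 4.3.6.6 ANCOVA, summaries, figure | BMI percentile |
| 4.3.6.8 opening | refers to percent-of-95th-percentile analyses and points back to 4.3.6.6 |
| 4.3.6.8 close | adds percentiles to the percent-of-95th listing |

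The last row shows that the SAP treats the two as separate variables. No visible sentence equates them.

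**2. Scale if percentile is analysed**

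Inputs: the 0.2-point Z-score reduction that defines a paediatric responder (Protocol 7.5.2 no. 7), used only as a yardstick, and assumed baseline Z-scores, because the documents give no paediatric baseline distribution. Mapping: percentile = 100 × Φ(Z). This treats Z-score and percentile as coming from one reference, whereas the SAP uses WHO 2007 for Z-score (4.3.5.1) and CDC 2000 for P95.

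Percentile change = 100 × [Φ(Z) − Φ(Z − 0.2)]

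| Assumed baseline Z | Calculation | Points |
|---|---|---|
| 1.7 | 100 × (0.95543 − 0.93319) | 2.22 |
| 2.0 | 100 × (0.97725 − 0.96407) | 1.32 |
| 2.5 | 100 × (0.99379 − 0.98928) | 0.45 |
| 3.0 | 100 × (0.99865 − 0.99744) | 0.12 |

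The ratio between the first and last rows is 2.22 / 0.12, about 18.

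**3. The same question for a fixed BMI loss**

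To avoid mixing references, take a 10% BMI fall at fixed age and sex with Z = [(BMI/M)^L − 1] / (L × S). Three assumed parameter sets (L, M, S) were used: (−2.0, 17.0, 0.13), (−2.3, 19.0, 0.135) and (−2.0, 20.5, 0.14). They are illustrative and are not taken from the documents.

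| Baseline P95 | P95 after a 10% fall | Percentile fall, range over the three sets |
|---|---|---|
| 100 | 90 | 6.3 to 8.0 |
| 120 | 108 | 1.4 to 1.5 |
| 140 | 126 | 0.37 to 0.46 |
| 160 | 144 | 0.13 to 0.19 |

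P95 = 100 × BMI / (BMI at the 95th percentile), so a 10% fall is a 10% relative fall at every baseline. On the percentile scale the same loss nearly vanishes in severe obesity.

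**The case against.** The strongest reply is that P95 is what the sponsor means. P95 is the only new variable that 4.3.6.6 derives. It is the one listed for missing-data handling, imputation and baseline summaries, and the opening of 4.3.6.8 calls the 4.3.6.6 analyses percent-of-95th-percentile analyses. On that reading, percentile is shorthand carried over from the protocol and the ceiling does not arise. This stands as evidence of intent, but it does not settle the text: the model, summaries and figure still name the other variable, and the endpoint wording in the protocol and SAP 1.4.1 would be wrong. SAP Section 5, where such a clarification might be recorded, is redacted, so its absence from the visible text is not counted against the plan.

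Three stronger readings are tempting and are not supported:

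- *The trial is blind to benefit in severely obese children.* It is not. Z-score is analysed alongside percentile in the same endpoint. It also drives the 0.2-point responder endpoint and the paediatric part of the first key secondary endpoint. Children also contribute to the primary percent change in BMI.
- *The percentile analysis cannot be run on imputed data.* It can. Percentile follows from imputed BMI, age and sex, and 4.3.6.8 already needs below-95th-percentile status in each imputed dataset. Its absence from the imputation lists bears on intent, not feasibility.
- *The loss of sensitivity is a known, very large factor.* Its size depends on baseline severity, which the documents do not give. More extreme assumed baselines produce larger ratios, but these would not be estimates for this trial.

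**Conclusion.** SAP 4.3.6.6 does not consistently identify its analysed variable. Followed literally, it tests a rank confined to 95-100 at screening, on which equal responses count far less in the most severely obese: about 18-fold less at Z = 3.0 than at Z = 1.7 for a 0.2-point fall, under the assumed baselines and normal mapping. If P95 is intended, which the balance of the SAP favours, the analysis is sound and the endpoint is mislabelled.

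The reach is limited. This is one of two outcomes in one other secondary endpoint, outside the fixed-sequence testing in SAP 3.7. Under the literal reading the scale would tend to hide a benefit, not create one. The correction is worth making because it either changes the reported result or corrects its name.

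**What to change.** In SAP 4.3.6.6, state that the ANCOVA, by-visit summaries and figure use change from baseline in BMI as a percent of the CDC 95th percentile (P95), derived from the imputed weights for the ANCOVA and from observed values for the summaries and figure. Align the endpoint wording in SAP 1.4.1, and in Protocol Table 3, the synopsis and 7.5.2 no. 6 at the next amendment. Keep raw percentile for the below-95th-percentile responder endpoint and the listing.

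If the sponsor does mean raw percentile, the SAP should say so, add its derivation from the imputed data, and justify a linear model on a bounded scale.

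The cost is a few sentences. P95 is already derived and imputed, no new data are needed, and the testing hierarchy is untouched. The one drawback is a departure from the protocol's endpoint wording, to be recorded as a change in SAP Section 5.1. Protocol Section 7 allows the SAP to modify planned analyses and calls for an amendment only for major changes to the primary endpoint or its analysis, so the SAP correction need not wait.
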